6.4. Other Endpoint(s)

6.4.1. Change from Baseline in Insulin, Glucagon and C-Peptide AUC₀₋₄

- Estimand strategy: Not applicable
- Analysis set: Pharmacodynamic Population Set
- The natural log-transformed of the relative change from baseline at the end of the study will be included in an ANCOVA model, as described in [Section 5.2.5](#), for each measure separately. The adjusted geometric LSMMeans and adjusted geometric LSMeans differences to placebo (with 90% confidence intervals) will be calculated and plotted.

Absolute values and percent change from baseline will be summarized descriptively by treatment and day as described in [Section 5.2.1](#).

6.4.2. Change from Baseline in Fasting Plasma Glucose, Fasting Plasma Insulin and HOMA-IR

- Estimand strategy: Not applicable
- Analysis set: Pharmacodynamic Population Set

Absolute values and change from baseline will be summarized descriptively by treatment and timepoint (when applicable) as described in [Section 5.2.1](#).

The change from baseline over time for FPG will be included in an MMRM model as described in [Section 5.2.3](#). The LSMMeans and LSMeans differences to placebo (with 90% confidence intervals) will also be plotted.

The change from baseline over time for FPI and HOMA-IR will be included in an ANCOVA model, as described in [Section 5.2.4](#), for each measure separately. The LSMeans and LSMean differences to placebo (with 90% confidence intervals) will also be plotted.

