### 9.3. Statistical Analyses

The SAP will be developed and finalized before any analyses are performed and will describe the analyses and procedures for accounting for missing, unused, and spurious data. This section is a summary of the planned statistical analyses of the primary and secondary endpoints.

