1. VERSION HISTORY

Table 1. Summary of Changes

Version/ Date	Associated Protocol Amendment	Rationale	Specific Changes
1 14 th Jan 2022	N/A	
 Original protocol 	N/A
2 28 th Jul 2022	N/A	
 Based on data review before database release, SQE (#PR2205605) was opened regarding confirmed aberrant glucose values reported by the site. SAP amendment is supported by DMB02 SOP and QMS-01 SOP Repeated wording for summarization of change from baseline on safety laboratories Listings of laboratory parameter of interest should only be listed/ Alignment with C3991002 outputs using Pfizer standards for reporting Physical examination data is not collected in this study 	
Impacted sections of SAP V1:
 
Section 3.3.1: reference to glucose AUC₀₋₄ removed
 
Section 3.3.4 - Change from baseline in MDG - removed
 
Section 5.3.5: reference to glucose AUC₀₋₄ and AUC₂₄ removed
 
Section 6.3.1: reference to glucose AUC₀₋₄ removed
 
Section 6.3.4: entire section removed
 
Section 3.4.1.2 removed
 
Section 6.7.1: Focused Laboratory Summaries on Endpoints of Interest removed
 
Section 6.7.2: Entire section removed

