2.1. Modifications to the Analysis Plan Described in the Protocol

The following endpoints

- *The MDG will be computed by $AUC_{24/24}$ hour.*
- *The $AUC_{(0-4)}$ for glucose will also be calculated.*

as described in Section 9.3.4 of the protocol has been removed due to aberrant glucose values (see [Version History](#)).

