2.3. Study Design

The purpose of this study is to evaluate the safety, tolerability, and PK of multiple doses of PF-07081532 in participants with T2DM, inadequately controlled on metformin. The study may also enroll non-diabetic participants with obesity.

The study will also assess the effect on PD biomarkers, including MDG.

[figure not shown]
This is a randomized, double-blind (investigator- and participant- blind), sponsor-open, placebo-controlled, multiple oral dose-escalating study of PF-07081532.

In this study, adult participants with T2DM inadequately controlled on metformin will be enrolled and will receive PF-07081532 or placebo daily, for 42 days.

- Enrollment in 3 cohorts is planned with approximately 12 participants (9 PF-07081532: 3 placebo) per cohort.

A sample dosing scheme is provided below. Dosing in Cohort 1 will be conducted as shown. Increments in doses and duration of dosing at each step for subsequent cohorts, as well as the number of cohorts conducted, may be adjusted based on emerging data. The dosing scheme for each cohort will be provided in writing prior to its initiation.

Figure 1. Dose Titration Scheme

If a participant does not tolerate dose increment to the next dose level, as determined by the investigator and with notification to the sponsor, the participant may be reverted to the previously tolerated dose level. Following this dose modification, 2 separate attempts at increasing the dose to the next dose level are permitted, per investigator discretion. If, per investigator assessment, unacceptable intolerance (eg, severe vomiting) occurs shortly following dose administration, the dose will not be re-administered on the same day, and the participant may resume dosing at the current dose level at the next scheduled dosing time. Participants whose dose level is tolerability-limited may continue in the study for the intended duration of their assigned cohort at their own individual MTD, as judged to be appropriate by the PI and sponsor.

The planned cohorts in the study (Cohorts 1-3) may be conducted concurrently, partially overlapping or sequentially. The sponsor may decide not to conduct all planned cohorts, if it is judged that study objectives have been met. Up to 3 additional cohorts may be enrolled if judged necessary to meet the study objectives. One or more of the study cohorts may be conducted in non-diabetic participants with obesity.

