3.3.2. Change from Baseline in Fasting Plasma Glucose, Fasting Plasma Insulin and HOMA-IR

The change from baseline to all post-dose timepoints as specified in the schedule of activities will be calculated.

Remark: Where triplicate fasting plasma insulin (FPI) are assessed, the average of the three measurements will be calculated to be reported at each timepoint and used to derive HOMA-IR. *When three assessments are performed at baseline, FPI baseline will be the average of the three values.*

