5.3.2. Deviations, Missing Concentrations and Anomalous Values

In summary tables and plots of median profiles, statistics will be calculated having set concentrations to missing if 1 of the following cases is true:

1. A concentration has been collected as ND (ie, not done) or NS (ie, no sample),
2. A deviation in sampling time is of sufficient concern or a concentration has been flagged anomalous by the pharmacokineticist/clinical team.

Note that summary statistics will not be presented at a particular time point if more than 50% of the data are missing.

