5.3.5. Pharmacodynamic Parameters

For baseline AUC₀₋₄ calculations, if participants have a missing baseline (ie, Day -1) 0 hour value, no imputation will be made. No imputation will be made for other missing values.

AUC₀₋₄ will only be calculated in any participant with at least the first, last, and 75% of the total number of samples within the given interval available. Nominal times will be used in the calculation. No imputation for missing values will be conducted for these PD endpoints.

If the concentrations are below the limits of quantification such values will be truncated at the limit of quantification for all summaries and analyses, and will appear as reported in all listings.

The same principles apply to the analyses of all other PD endpoints.

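### Does SAP version 2, amended for aberrant glucose values, need a spurious-data rule before it can keep FPG and HOMA-IR?

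*SAP*

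**What the plan says.** Protocol 9.3 promises that the SAP "will describe the analyses and procedures for accounting for missing, unused, and spurious data".

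The SAP version history explains that version 2 followed a data review before database release, when a numbered quality event "was opened regarding confirmed aberrant glucose values reported by the site". It cites two SOPs in support and lists the impacted sections of version 1. Those entries remove glucose AUC0-4, glucose AUC24 and MDG. SAP 2.1 confirms that the MDG and glucose AUC0-4 plan of protocol 9.3.4 "has been removed due to aberrant glucose values".

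Three uses of fasting glucose remain:
- FPG change from baseline, by MMRM (SAP 6.4.2: "The change from baseline over time for FPG will be included in an MMRM model as described in" Section 5.2.3).
- HOMA-IR, which protocol 8.9.2 and 9.3.4 derive from FPG and FPI, by ANCOVA (SAP 6.4.2).
- Baseline FPG in the SAP 6.6.1 table.

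SAP 3.3.2 defines FPG change in one line: "The change from baseline to all post-dose timepoints as specified in the schedule of activities will be calculated". It does not name the sample.

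Two data-handling rules are relevant. SAP 5.3.2 opens "In summary tables and plots of median profiles, statistics will be calculated having set concentrations to missing" and applies when a concentration is flagged as anomalous. SAP 5.3.5 covers missing samples, AUC completeness and values below quantification for PD data, and ends "The same principles apply to the analyses of all other PD endpoints".

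**The concern.** The plan was amended because glucose data were faulty, yet it still analyses glucose. A reader of the SAP alone cannot tell whether FPG and HOMA-IR are free of the fault that removed the other two endpoints.

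No written rule closes that question. SAP 5.3.5 does not mention aberrant values. SAP 5.3.2 sits among the PK rules and acts on summary tables and median plots, so even a generous reading does not carry it into the MMRM or ANCOVA. SAP 5.3.4 imports an anomalous-value rule by name for the 4-beta-hydroxycholesterol ratio; 5.3.5 has no matching import for glucose.

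The arithmetic adds to the worry. FPG may be the 0H sample of the same protocol Table 2 series that fed the deleted endpoints. An error at 0H is almost averaged away in those endpoints but enters FPG whole, and HOMA-IR through it. The impacted-sections list might also be incomplete, because SAP 2.3 still says "The study will also assess the effect on PD biomarkers, including MDG".

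**Working it through.** **1. Is there evidence that a fasting value was affected?** The documents give no sample type, day, participant or cohort for the aberrant values. The evidence on scope is indirect:
- The version history lists sections 3.3.1, 3.3.4, 5.3.5, 6.3.1 and 6.3.4 of version 1 for the glucose deletions. Section 3.3.2, which holds FPG and HOMA-IR, is absent. The authors opened 5.3.5 for this event and left FPG alone, which reads as a decision about scope.
- The MDG sentence in SAP 2.3 is design text carried over from the protocol rationale, and SAP 2.1 overrides it. The glucose endpoints still shown in SAP 2.2 are likewise restated protocol objectives. These are clerical leftovers and do not show that an analysis section was missed.

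**2. What do the sampling weights suggest?** Inputs: protocol Table 2 times 0, 0.25, 0.5, 1, 1.5, 2, 3, 4 H (8 samples), then 6, 8, 10, 12, 16, 24 H (14 in all). MDG is AUC24/24 (protocol 9.3.4). The linear trapezoid is assumed. The weight of the 0H sample is half the first interval divided by the total length:
- 0-4 H mean: (0.25/2)/4 = 0.125/4 = 3.1%.
- 24-hour mean: 0.125/24 = 0.52%.
- FPG, if it is that sample: 100%.

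An error of 100 mg/dL at 0H alone would therefore move the 4-hour mean by 3.1 mg/dL and MDG by 0.5 mg/dL. That would hardly justify deleting both endpoints. The deletion points to later samples or to the whole series. A fault across the series, 0H included, is not excluded.

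**3. Is FPG the 0H sample of that series?** Not certainly. Protocol Table 2 takes a fasting 0H plasma glucose in all participants, with Day 28 assured only for Cohort 1. Fasting plasma glucose is also a safety chemistry test (protocol Table 6), drawn on Days -1, 28 and 42 and on other visits. SAP 6.4.2 gives FPG a repeated-measures model, while FPI and HOMA-IR, scheduled on Days -1 and 42, get ANCOVA. That fits safety-laboratory glucose. It also fits the Table 2 series wherever Day 28 was run.

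**4. How much could it matter?** The plan states no figure to reproduce, since the sample size was chosen empirically. All of the following are assumptions: baseline SD 40 mg/dL, slope of Day 42 on baseline 0.7, residual SD 20 to 30, errors of 50 or 100 mg/dL, and three cohorts of 9 active with pooled placebo of 3 × 3 = 9. Simulation of the Day 42 ANCOVA (8,000 runs per setting) gave the half-widths below; simple arithmetic gives the shifts.
- Day 42 error in one active participant: shift = error/9, so 50/9 = 5.6 and 100/9 = 11.1 mg/dL.
- 90% CI half-width, clean data: 16.1 (SD 20) or 24.2 (SD 30).
- Half-width with a 100 mg/dL error: 21.0 or 27.6. As a check for SD 20, with 36 participants, 4 group means and one slope there are 31 residual df. The residual sum of squares rises from 31 × 400 = 12,400 by about 100² × 8/9 = 8,889, so the residual SD becomes √(21,289/31) = 26.2, and 16.1 × 26.2/20 = 21.1.
- Baseline error of 100 mg/dL: the within-group baseline sum of squares goes from 32 × 1,600 = 51,200 to 60,089, so the slope shrinks to 0.7 × 51,200/60,089 = 0.596. The shift is -0.596 × 11.1 = -6.6.
- Value set to missing: no shift; half-width 16.6 or 25.0, and 16.6/16.1 = 1.03, or about 3% wider.

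On one complete two-visit data set (9 versus 9), the unstructured MMRM and the per-visit ANCOVA gave the same Day 42 difference and standard error (-1.1375, SE 11.101), so the ANCOVA figures serve for the MMRM when data are complete. The lower end of the range is nil.

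**The case for a change.** The strongest case for a change is that omission from a list is not a statement. Protocol 9.3 commits the SAP to procedures for spurious data, and version 2 was the obvious place to record that fasting results had been checked. One line would cost nothing. If a fasting value was wrong, keeping it could bias a cohort's difference, while dropping it costs about 3% in precision. The study is also sponsor-open, so leaving value-level exclusions to later judgement is less comfortable than under a full blind.

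Part of this stands. The SAP does not name the FPG sample, does not state the scope of the quality event, and has no anomalous-value rule that reaches the FPG or HOMA-IR models.

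The rest is weaker:
- The amendment is itself a procedure for spurious data: a review before database release, a quality event, cited SOPs and named deletions. Value-level handling may lie in those records, which are not among the documents, so its absence from the SAP does not show that it is undefined.
- Protocol 9.3 describes itself as a summary for primary and secondary endpoints. The sentence about the SAP is not itself so limited, but it is thin ground for alleging a breach over an exploratory measure.
- A rule fixed now on the 0H sample could name the wrong source. If it covered only FPG and HOMA-IR, the same result could be missing there and still counted in the laboratory summaries of SAP 6.2.1.5.

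**Conclusion.** The gap in the text is real, but it is missing detail and not an error in the analysis. Following the plan as written is not shown to give a wrong result. The most natural reading is that the review found the profile-based endpoints unusable and left fasting glucose outside its scope. If a fasting value had been confirmed as wrong, an analyst would ordinarily set it to missing for FPG, HOMA-IR and their baselines and keep it in the listings, without needing the SAP to say so.

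The size runs from nil to the figures above (at most 11.1 mg/dL for one 100 mg/dL error among 9 active participants). Every non-zero figure rests on assumed SDs, slope and error sizes; the documents support none of them. FPG and HOMA-IR are exploratory, protocol 9.1 rules out hypothesis testing, and protocol 9.3.4 allows exploratory analyses to be left out of the study report. The secondary PK results do not use glucose. Fasting glucose is also one of the safety laboratory tests, but nothing shows those results to be at fault. No change to the plan is needed.

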6.4.3. Change from Baseline in HbA1c

- Estimand strategy: Not applicable
- Analysis set: Pharmacodynamic Population Set

Absolute values and change from baseline will be summarized descriptively by treatment and timepoint as described in [Section 5.2.2](#)

The change from baseline over time will be included in an MMRM model as described in [Section 5.2.3](#). The LSMeans and LSMean differences to placebo for each timepoint (with 90% confidence intervals) will be plotted.

6.4.4. 4- β -hydroxycholesterol/Cholesterol Ratio

The percent change from baseline to all post-dose timepoints as specified in the SoA will be calculated.

- Estimand strategy: Not applicable
- Analysis set: PD Population Set

Absolute values, and percent change from baseline will be summarized descriptively by treatment and day as per [Section 5.2.1](#).

The percent change from baseline over time will be analyzed with an ANCOVA model as described in [Section 5.2.5](#). The LSMeans and LSMean differences to placebo (with 90% confidence intervals) will be plotted. Results of this analysis may be not included in the CSR.

6.5. Subset Analyses

Not applicable

6.6. Baseline and Other Summaries and Analyses

Where relevant, data will be reported in accordance with the sponsor reporting standards.

6.6.1. Baseline Summaries

A baseline table (or separate tables, as required) summarizing the following will be produced by treatment group and overall (T2DM and non-diabetic obesity, summarized separately): HbA1c; fasting plasma glucose; systolic blood pressure; diastolic blood pressure; pulse rate; and metformin total daily dose (for T2DM participants only).

6.6.2. Study Conduct and Participant Disposition

Participant evaluation groups will show participant disposition for each phase of the study (screening, double-blind treatment and follow-up) and will additionally show which participants were analyzed for safety, for PK and for tertiary endpoints. Frequency counts and percentages will be supplied for participant discontinuation(s) by treatment group and overall.

CCI

6.6.4. Concomitant Medications and Nondrug Treatments

All prior and concomitant medication(s) as well as non-drug treatment(s) will be reported according to current sponsor reporting standards.

6.6.5. Discontinuations

Participant discontinuations, temporary discontinuations or dose reductions due to adverse events will be detailed and summarized by treatment group and overall.

Data will be reported in accordance with the sponsor reporting standards.

6.7. Safety Summaries and Analyses

Not applicable

7. INTERIM ANALYSES

7.1. Introduction

No formal interim analysis will be conducted for this study. As this is a sponsor-open study, the sponsor may conduct unblinded reviews of the data during the course of the study for the purpose of safety assessment, facilitating dose selection decisions, facilitating PK/PD modeling, and/or supporting clinical development.

7.2. Interim Analyses and Summaries

Not applicable.

8. REFERENCES

3. ICH Harmonised Guideline E9 (R1); Estimands and Sensitivity Analysis in Clinical Trials; 16 June 2017.
4. Pfizer Guidance for Evaluation of QT / QTc Interval Prolongation and Proarrhythmic Potential for Non-antiarrhythmic Drugs; Members of the Cardiovascular Safety & Advisory Council (CVSAC); January 26, 2018.

APPENDICES**Appendix 1. Statistical Methodology Details**Example SAS code for MMRM Model:

```
proc mixed data = dataset method=reml;
    class subject treatment time;
    model cfb = treatment base time base*time time*treatment / ddfm=kr residual
outp=resid_out;
    repeated time /subject=subjid type = un;
    lsmeans treatment*time/diff cl alpha=0.1;
    ods output lsmeans=lsmeans_out;
    ods output diffs=diffs_out;
run;
```

Example SAS code for Cumulative Incidence Plots:

```
proc lifetest data = dataset method=km plots=cif(test) outcif=cifatrisk intervals=0 to 20 by 2;
    strata treatment;
    time day*censor(1)/eventcode=0;
run;
```

NOTE: the censor variable has a value = 1 when the related time is censored and has a value = 0 when the event of interest occurs. There should be no other values available for this censored variable in this dataset (including missing values). If required, missing observations should be removed prior to analysis.

Appendix 2. Categorical Classes for ECG and Vital Signs of Potential Clinical Concern

Categories for QTcF

Absolute value of QTcF (msec)	>450 and ≤480	>480 and ≤500	>500
Increase from baseline in QTcF (msec)	>30 and ≤60	>60	

Categories for PR and QRS

PR (ms)	max. ≥300	
PR (ms) increase from baseline	Baseline >200 and max. ≥25% increase	Baseline ≤200 and max. ≥50% increase
QRS (ms)	max. ≥140	
QRS (ms) increase from baseline	≥50% increase	

Categories for Vital Signs

Systolic BP (mm Hg)	min. <90	
Systolic BP (mm Hg) change from baseline	max. decrease ≥30	max. increase ≥30
Diastolic BP (mm Hg)	min. <50	
Diastolic BP (mm Hg) change from baseline	max. decrease ≥20	max. increase ≥20
Supine pulse rate (bpm)	min. <40	max. >120

Appendix 3. List of Abbreviations

Abbreviation	Term
Abs	Absolute
AE	adverse event
ANCOVA	analysis of covariance
ANOVA	analysis of variance
ATC	Anatomic Therapeutic Chemical
AUC	area under the curve
BA	Bioavailability
BE	Bioequivalence
BLQ	below the limit of quantitation
BOCF	baseline observation carried forward
BP	blood pressure
CDARS	Clinical Data Analysis and Reporting System (of US Food and Drug Administration)
CI	confidence interval
C _{max}	maximum observed concentration
CMH	Cochran-Mantel-Haenszel
CRF	case report form
CSR	clinical study report
DMC	data monitoring committee
EAC	event adjudication committee
ECG	electrocardiogram
E-DMC	external data monitoring committee
FAS	full analysis set
FDA	Food and Drug Administration (United States)
GCP	Good Clinical Practice
GLIMMIX	generalized linear mixed-effects model with repeated measures
GMC	geometric mean concentration
GMFR	geometric mean fold rise
GMR	geometric mean ratio
GMT	geometric mean titer
ICD	informed consent document
ICH	International Council for Harmonisation
IRC	internal review committee
IST	independent statistical team
ITT	intent-to-treat
LLOQ	lower limit of quantitation
LOCF	last observation carried forward
LOD	limit of detection
LS	least-squares
LSM	least-squares mean
MAR	missing at random

Abbreviation	Term
MedDRA	Medical Dictionary for Regulatory Activities
mITT	modified intent-to-treat
MMRM	mixed-effects model with repeated measures
MNAR	missing not at random
N/A	not applicable
NNB	number needed to benefit
NNH	number needed to harm
NNT	number needed to treat
NOAEL	no-observed-adverse-effect level
PD	pharmacodynamic(s)
PK	pharmacokinetic(s)
PP	per-protocol
PPAS	per-protocol analysis set
PRO	patient-reported outcome
PT	preferred term
QTc	corrected QT
QTcF	corrected QT (Fridericia method)
qual	qualitative
RCDC	reverse cumulative distribution curve
RR	relative risk
SAE	serious adverse event
SAP	statistical analysis plan
SD	standard deviation
SGS	Statistical Guidance Standards
SOP	standard operating procedure
SUSAR	suspected unexpected serious adverse reaction
TA	therapeutic area
ULN	upper limit of normal
WHO	World Health Organization
WHODD	World Health Organization Drug Dictionary
